8.3.1.8 Medical Outcomes Study (MOS) sleep scale

The MOS Sleep Scale will be used by the study participant to measure specific aspects of sleep. The frequency with which each sleep problem has been experienced during the previous 4 weeks is rated on a 5-point scale ranging from “none of the time” to “all of the time”.

Out of the 12 sleep problems/items covered by the MOS sleep scale, only items relevant to derive the Sleep Disturbance and the Sleep Problems Index II subscales will be considered in this

study. **Table 8–3** below describes which items are used for each sleep subscale of interest, and which items need to be reversed scored (these are indicated with an R in brackets).

Table 8–3: MOS sleep subscales

Subscale name	Number of items	Item scores
Sleep Disturbance	4	1, 3 (R), 7 (R), 8 (R)
Sleep Problems Index II	9	1, 3 (R), 4, 5 (R), 6 (R), 7 (R), 8 (R), 9 (R), 12

Note: (R) refers to a reversed item.

The subscale scores are created by averaging the respective rescaled item scores. Scales with at least 1 item answered can be used to generate a scale score. Items that are missing are not taken into account when calculating the scale scores. Scores represent the average for all items in the scale that the respondent answered.

Prior to averaging, each item score is transformed linearly to range from 0 to 100. Higher scores indicate more of the attribute implied by the scale name (eg, more sleep disturbance or more sleep problems).

QualityMetric Health OutcomesTM Scoring Software will be used to calculate the domains of Sleep disturbance and Sleep problems Index II.

8.3.1.9 Functional Assessment of Chronic Illness Therapy (FACIT)-Fatigue subscale

The FACIT-Fatigue is a 40-item measure that assesses self-reported fatigue and its impact upon daily activities and function within the past 7 days. The scale consists of 5 subscales (physical well-being, social/family well-being, emotional well-being, functional well-being, and fatigue). The fatigue subscale will be the only domain used in this study. It is composed of 13 items, all scored from 0 (Not at all) to 4 (Very much). The FACIT-Fatigue subscale score ranges from 0 to 52 with 0 being the worst possible score and 52 being the best possible score. To obtain a score from 0 to 52, all negatively worded questions have to be recoded, so that responses range from worst (0) to the best (4) outcome. This implies that the values to all questions (except for

The FACIT-Fatigue subscale score is then obtained by summing up the responses of all 11 reversed items and responses of item 7 and 8 with equal weight.

In cases where some answers are missing, a total score is re-scaled from the score of the answered items, so long as more than 50% of the items (ie, at least 7 of 13) were answered.

The formula to derive the FACIT-Fatigue subscale score is then:

$$FACIT - Fatigue = 13 \times \frac{\sum \text{Score of items}}{\text{number of item answered}}$$

8.3.1.10 Work Productivity and Activity Impairment Questionnaire-Specific Health Problem (WPAI-SHP)

The WPAI-SHP is a study participant-reported questionnaire that assesses study participant's employment status, work absenteeism, work impairment while working, overall work, and daily activity impairment attributable to a specific health problem.

Five out of 6 items of the WPAI-SHP are regrouped into the 4 dimensions (absenteeism, presenteeism, work productivity and activity impairment) with scores expressed as percentage, where higher numbers indicate greater impairment and less productivity (ie, worse outcomes) as described in the WPAI-SHP scoring rules.

The scoring rules for the WPAI-SHP are as follows:

Question 1 is a Yes/No question.

Questions Q5 and Q6 are measured on a 0 to 10 scale (0= no effect, 10= complete interference). In order to make data consistent and amenable to statistical analysis, the following counting rules will be applied to handle out of range and ambiguous answers of the WPAI-SHP. These rules will be applied prior to conducting any type of statistical analysis of the data. Due to the interrelation between certain questions of the WPAI-SHP, the priority order for implementing these specific counting rules is as in the listed order below.

- Employment status:
 - If (Q1=missing) and (Q2>0 or Q3>0 or Q4>0), then Q1=YES.
- Hours missed due to Ankylosing spondylitis:
 - If Q1 = NO, then Q2 = missing.
 - If (Q2 =0 or missing) and Q1 = missing, then Q2=missing.
- Hours missed due to other reasons:
 - If Q1 = NO, then Q3 = missing.
 - If (Q3 =0 or missing) and Q1 = missing, then Q3=missing.
- Hours actually worked:

- If Q1 = NO, then Q4 = missing.
- If (Q4 =0 or missing) and Q1 = missing, then Q4=missing.
- Work productivity:
 - If Q1 = NO, then Q5 = missing.
 - If (Q5 =0 or missing) and Q1 = missing, then Q5=missing.
 - If Q4=0, then Q5 = missing.

In the listings, the original values will be kept and displayed.

After implementing the missing data rules above for questions Q1 to Q5, the following four scores will be derived:

- Percent work time missed due to problem from the target disease:

$$\frac{Q2 \text{ hours}}{Q2 \text{ hours} + Q4 \text{ hours}} * 100, Q2 \text{ hours} + Q4 \text{ hours} \neq 0$$

- Percent impairment while working due to problem from the target disease:

$$\frac{Q5 \text{ score}}{10} * 100$$

- Percent overall work impairment due to problem from the target disease:

$$\left[\frac{Q2 \text{ hours}}{Q2 \text{ hours} + Q4 \text{ hours}} + \left(1 - \frac{Q2 \text{ hours}}{Q2 \text{ hours} + Q4 \text{ hours}} \right) * \frac{Q5 \text{ score}}{10} \right] * 100$$

- Percent activity impairment due to problem from the target disease:

$$\frac{Q6 \text{ score}}{10} * 100$$

WPAI scores are based on 1-item (presenteeism, activity impairment), 2-items (absenteeism) and multiple items (overall work productivity). A score cannot be calculated if there is a missing response to the corresponding item.

Because questions 2 to 6 are only relevant when the answer to question 1 is Yes, and because imputation of results is questionable without knowing the answer to question 1, only observed case analysis will be performed for this endpoint.

8.3.1.11 **Tender joint count (TJC) and swollen joint count (SJC)**

Each of the following 44 joints will be assessed for tenderness:

- Upper body (4) - bilateral sternoclavicular, and acromioclavicular joints.
- Upper extremity (26) - bilateral shoulders, elbows, wrists (includes radiocarpal, carpal and carpometacarpal bones considered as a single unit), metacarpophalangeal (I, II, III, IV, and V), thumb interphalangeal, and proximal interphalangeal (II, III, IV, and V).
- Lower extremity (14) - bilateral knees, ankles, and metatarsophalangeals (I, II, III, IV, and V).

All of these 44 joints will also be assessed for swelling.

Each of the joints can be graded as follows by the assessor:

- Permanently not assessable
- Temporarily not assessable
- Asymptomatic
- Tender only
- Swollen only
- Tender and swollen

Permanently not assessable joints will be considered missing for both tender and swollen joint counts at the visit at which the grading was recorded and all subsequent visits.

For the statistical analysis, swelling and tenderness will be each graded on a 2-point scale as described below in [Table 8-4](#):

Table 8-4: Swelling and tenderness grading

Grade	Tenderness response (44)	Swelling response (44)
0	Not tender	None
1	Tenderness present	Detectable synovial thickening

The joint graded by the assessor will then have its grade mapped as follows:

- The “Tender only” joints will correspond to a tenderness response of 1, and a swollen response of 0.
- The “Swollen only” joints will correspond to a swollen response of 1, and a tenderness response of 0.
- The “Tender and swollen” joints will correspond to a swelling and tenderness response of 1.

In addition, injected joints will be counted as swollen and tender (ie, swelling and tenderness grading of 1) from the date of injection up to 1 year after injection.

Dactylitic digits will be identified as follows and the joints will be counted as follows:

- Fingers 2-5: Swelling Distal Interphalangeal Joint x (side), Swelling Proximal Interphalangeal Joint x (side), Swelling Metacarpophalangeal Joint x (side) – if they are in any of the gradings ‘swollen only’ or ‘tender and swollen’ or ‘injected’ then only 1 finger will be added to the swollen joint count
- Toes 1-5: Swelling Interphalangeal Joint x (side), Swelling Metatarsophalangeal Joint x (side) – if they were in any of gradings ‘swollen’ or ‘tender and swollen’ or ‘injected’ then only 1 toe will be added to the swollen joint count

The tender joint count and swollen joint count are weighted joint counts. If there are missing observations in the tender or swollen joint assessments (TJ and SJ, respectively), then the remaining observations will be assessed and weighted by the number of the assessed joints (AJ) as shown below:

$$TJC = n \times \frac{\sum_{i=1}^n TJ}{\sum_{i=1}^n AJ}$$

$$SJC = n \times \frac{\sum_{i=1}^n SJ}{\sum_{i=1}^n AJ}$$

Where n represents the number of total joints.

However, if a joint is missing at Baseline, then that joint will be set to missing throughout the study. If more than 50% of the planned tender joint assessments (ie, more than 22) or 50% of the swollen joint assessments (ie, more than 22) are missing at any post-Baseline visit, then no imputation will be done and the total TJC or SJC will be set to missing for that visit.

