8.3.3 Additional statistical analysis of selected other efficacy variables

Although statistical testing is not planned for other efficacy variables per protocol, statistical testing and inferential statistics are of interest for selected endpoints. As these tests are not part of the multiplicity-controlled procedure, the associated p-values are considered nominal and should not be used for inference. Similarly as described in Section 8.2.3, statistical tests and calculation of inferential statistics will be performed for the following selected other efficacy endpoints:

- ASAS40 at Week 1, Week 2, Week 4, Week 8, Week 12
- ASAS40 in the TNF alpha inhibitor-naïve study participants at Week 1, Week 2, Week 4, Week 8, Week 12
- ASAS20 at Week 1, Week 2, Week 4, Week 8, Week 12
- PGADA at Week 1, Week 2, Week 4, Week 8, Week 12, Week 16
- Total spinal pain at Week 1, Week 2, Week 4, Week 8, Week 12, Week 16
- Nocturnal spinal pain at Week 1, Week 2, Week 4, Week 8, Week 12
- BASFI at Week 1, Week 2, Week 4, Week 8, Week 12
- Mean BASDAI Q5 and Q6 score at Week 1, Week 2, Week 4, Week 8, Week 12, Week 16
- BASDAI at Week 1, Week 2, Week 4, Week 8, Week 12,
- BASDAI50 at Week 1, Week 2, Week 4, Week 8, Week 12, Week 16
- CRP at Week 1, Week 2, Week 4, Week 8, Week 12, Week 16
- ASDAS-CRP at Week 16
- MASES at Week 16
- Enthesitis free state at Week 16
- TJC at Week 16
- SJC at Week 16
- FACIT-Fatigue at Week 16
- WPAI at Week 16
- ASspiMRI at Week 16
- SPARCC at Week 16

The same models as described in Section 8.2.3 will be run, and results will be presented in one single table together with the results for secondary endpoints.

In addition, the Week 16 results from the primary analysis for the primary endpoint ASAS40, and key secondary endpoints in the hierarchy (ASAS20, BASDAI, BASFI, nocturnal spinal pain) will also be included in this table.

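### WPAI overall work impairment is lost for employed participants who worked no hours because of their disease, although the SAP's own formula gives 100%

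*SAP*

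**What the plan says.** Section 8.3.1.10 of the SAP lists counting rules for the WPAI-SHP items, to be applied in the order given. The last one, under work productivity, reads "If Q4=0, then Q5 = missing". It makes no exception for participants whose hours were lost to the disease (Q2>0).

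The order of derivation is explicit: "After implementing the missing data rules above for questions Q1 to Q5, the following four scores will be derived". One of these is "Percent overall work impairment due to problem from the target disease", whose formula uses Q2, Q4 and Q5. The section describes the scores as resting on one item, or on "2-items (absenteeism) and multiple items (overall work productivity"), and adds: "A score cannot be calculated if there is a missing response to the corresponding item". The scores are percentages "where higher numbers indicate greater impairment and less productivity (ie, worse outcomes"), so 100% is the worst possible value.

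For missing scores, the section says that "only observed case analysis will be performed for this endpoint". Footnote d of Table 4–1 likewise rules out multiple imputation for the change from Baseline in WPAI-SHP. Section 8.3.3 lists "WPAI at Week 16" among the other efficacy variables that receive a statistical test with a nominal p-value.

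**The concern.** Setting Q5 to missing is sensible for presenteeism, because a person who worked no hours cannot rate impairment while working. The difficulty is that the same recoding carries into the overall score, where Q5 has no influence once all of Q2+Q4 is lost time. The plan then discards a value that its own formula fully determines, and that value is the maximum of the scale.

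The loss is tied to the outcome. A participant fully absent at Baseline who returns to work has no Baseline score, so a large improvement disappears. A participant who becomes fully absent by Week 16 has no Week 16 score, so a large deterioration disappears. With observed cases only, nothing later in the analysis restores either one. At stake are the mean overall impairment at each visit, the change from Baseline, and the Week 16 comparison.

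**Working it through.** **Inputs, all from SAP section 8.3.1.10.** Q1 is employment, Q2 hours missed because of the disease, Q3 hours missed for other reasons, Q4 hours worked, and Q5 impairment while working (0 to 10).

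- Absenteeism = Q2/(Q2+Q4) × 100, defined when Q2+Q4 is not 0
- Presenteeism = Q5/10 × 100
- Overall = [Q2/(Q2+Q4) + (1 − Q2/(Q2+Q4)) × Q5/10] × 100

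**Step 1: the formula at Q4=0 and Q2>0.** Then Q2/(Q2+Q4) = 1 and the weight on Q5 is 1 − 1 = 0. Overall = [1 + 0 × Q5/10] × 100 = 100%. Evaluated for every Q5 from 0 to 10 with Q2=40, the result is 100% each time.

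**Step 2: the SAP rules in their listed order, on example responses.**

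| Responses | Absenteeism | Presenteeism | Overall, SAP rules | Overall, formula alone |
|---|---|---|---|---|
| Q1=YES, Q2=40, Q4=0, Q5 blank | 100% | missing | missing | 100% |
| Q1=YES, Q2=40, Q4=0, Q5=7 | 100% | missing | missing | 100% |
| Q1 blank (recoded YES since Q2>0), Q2=40, Q4=0 | 100% | missing | missing | 100% |
| Q1=YES, Q2=10, Q3=30, Q4=0 | 100% | missing | missing | 100% |
| Q1=YES, Q2=39, Q4=1, Q5=0 | 97.5% | 0% | 97.5% | 97.5% |
| Q1=YES, Q2=20, Q4=20, Q5=5 | 50% | 50% | 75% | 75% |
| Q1=YES, Q2=0, Q3=40, Q4=0 | undefined | missing | missing | undefined (0/0) |

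The first four rows are lost although the formula gives 100%. One hour worked keeps a participant in at 97.5%; no hours worked drops them. The last row is rightly missing, because the denominator is zero.

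**Step 3: what this could do to a mean.** The SAP gives no employment rate, absence rate or WPAI mean, so these are illustrations on assumed inputs. Dropping a share f of participants changes the mean by f × (difference between the lost and the retained).

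- *Level at one visit.* Retained participants average 45% and a share f sits at 100%. The full mean is (1 − f) × 45 + f × 100, which is 46.1 for f=2%, 47.75 for f=5% and 50.5 for f=10%. The SAP rules report 45.
- *Fully absent at Baseline, then improving.* With f=3%, a 60-point improvement in those lost and 10 to 20 points in the rest, improvement is understated by 0.03 × (60 − 20) = 1.2 to 0.03 × (60 − 10) = 1.5 points.
- *Fully absent at Week 16.* With f=3%, a rise from 45% to 100% (+55) in those lost and the same 10 to 20 points of improvement in the rest, improvement is overstated by 0.03 × (55 + 10) = 1.95 to 0.03 × (55 + 20) = 2.25 points.

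The two kinds of loss act in opposite directions within an arm.

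**The case against.** Five points can be made for leaving the plan alone.

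1. No single sentence declares the overall score missing in this case. The result comes from reading three statements together, and the missing-item sentence speaks of one corresponding item without addressing an item with zero weight. This is true, but the combined reading is the natural one: the overall score is described as a multiple-item score, its formula contains Q5, and no exception is written. A programmer following the text would leave the score uncalculated.

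2. Full absence is still visible elsewhere. The same participants keep an absenteeism score of 100% and their activity impairment score. This stands and limits the point to one of the four scores.

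3. The size and sign of the bias are not known. This also stands. The illustrations rest on assumed inputs, each covers one kind of loss, and they concern one arm's mean. The Week 16 test compares arms in an ANCOVA adjusted for Baseline under the same rule in both arms, and no effect on the treatment difference has been shown.

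4. The endpoint is exploratory, outside the testing hierarchy, and its p-value is nominal. This stands and sets the severity.

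5. The section refers to the instrument's scoring rules, which are not at hand. The repair does not depend on them, because the value of 100% comes from the formula printed in the SAP.

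The SAP's stated reason for observed cases, that imputation is doubtful when employment is unknown, does not apply either. Employment is known here, or is recoded to YES because Q2>0, and nothing has to be imputed.

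**Conclusion.** The concern holds. Read as written, section 8.3.1.10 leaves overall work impairment missing for every participant-visit with Q2>0 and Q4=0, while its own formula gives exactly 100%. This conclusion rests only on the SAP's rules and algebra and needs no outside assumption.

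The effect on results cannot be computed from the document. On assumed shares of 3%, an arm's mean change moves by between 1 and just over 2 points, in a direction that depends on whether full absence occurs at Baseline or at Week 16; the net sign is open. The reach is one of four WPAI scores on an exploratory endpoint, so no primary or key secondary conclusion depends on it. It is a minor point, but a rule that gives a wrong result rather than a missing detail.

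**What to change.** Add one line to section 8.3.1.10, after the counting rules: when Q1 is YES (as reported or as recoded), Q2>0 and Q4=0, overall work impairment is set to 100%. Keep Q5, and so the presenteeism score, missing in that case. Keep the overall score missing when Q2 and Q4 are both 0, since the formula is then undefined. Apply the line at Baseline and at every later visit.

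The cost is one sentence in the SAP and one condition in the derivation program. It needs no new data and no imputation, and it changes no other score or analysis.

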^b Required only for by-visit summaries of variables whose value at Week 16 is part of the hierarchical testing procedure.

^c For variables with multiple categories, data will be summarized as observed with an additional missing row to capture missing data at a given visit.

^d MI will not be performed for the change from baseline in WPAI-SHP, change from baseline in EQ-5D-3L Utility Scores, change from Baseline in ASspiMRI-a (Berlin modification) score, or change from baseline in SPARCC score where only observed case analysis will be performed.

^e Performed only for components of the primary endpoint.

^f MI analysis will only be required for ASDAS status endpoint.

^g Last Observation Carried Forward (LOCF) will only be used for the secondary continuous endpoints in the hierarchy if the Reference-Based Multiple Imputation analyses do not converge.

In this section, two terms will be defined for binary endpoints:

- Binary endpoints derived based on one continuous measurement (eg, BASDAI50 at Week 16) will be called ‘non-composite binary endpoint’.
- Binary endpoints derived based on several continuous measurements (eg, ASAS40 at Week 16), will be called ‘composite binary endpoint’.

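### WPAI activity impairment is left out of multiple imputation for a reason that does not apply to it

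*SAP*

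**What the plan says.** SAP Section 8.3.1.10 describes the WPAI-SHP as covering employment status, absenteeism, impairment while working, "overall work, and daily activity impairment attributable to a specific health problem". Its counting rules set questions 2, 3, 4 and 5 to missing when question 1 is answered No. There is no such rule for question 6, and the section confirms where the rules stop: "After implementing the missing data rules above for questions Q1 to Q5, the following four scores will be derived". The fourth score, "Percent activity impairment due to problem from the target disease", is question 6 divided by 10 and multiplied by 100. The section also classes it as a one-item score: "WPAI scores are based on 1-item (presenteeism, activity impairment), 2-items (absenteeism) and multiple items (overall work productivity".

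The section then closes with a different account. It gives two reasons, "Because questions 2 to 6 are only relevant when the answer to question 1 is Yes" and "imputation of results is questionable without knowing the answer to question 1", and concludes that "only observed case analysis will be performed for this endpoint". Footnote d of Table 4-1 (Section 4.2.1) repeats this for the questionnaire as a whole: "MI will not be performed for the change from baseline in WPAI-SHP". Section 8.3.2 likewise lists WPAI-SHP among the variables exempt from the hypothetical-estimand imputation.

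**The concern.** Activity impairment is the one WPAI score that does not depend on having a job. The closing sentence of Section 8.3.1.10 nevertheless treats it as a work item and uses that to settle the missing-data method for all four scores.

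Two things follow. First, the method for activity impairment has no stated justification that fits it, although the SAP's usual method for a continuous endpoint is multiple imputation. Second, the section holds two incompatible statements about whether a non-worker's answer to question 6 counts, and a programmer could follow either. WPAI at Week 16 is on the Section 8.3.3 list of variables compared between arms with inferential statistics, so the ambiguity reaches a reported estimate and p-value.

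**Working it through.** The SAP gives no figure to reproduce here. The check is a trace of its own rules.

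**Step 1. Which scores depend on question 1?** From the counting rules and formulas in Section 8.3.1.10:

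| Score | Items used | Blanked when question 1 = No? |
|---|---|---|
| Work time missed | Q2, Q4 | Yes |
| Impairment while working | Q5 | Yes |
| Overall work impairment | Q2, Q4, Q5 | Yes |
| Activity impairment | Q6 | No |

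**Step 2. Trace one participant.** Take question 1 = No and, as an example, question 6 = 7. The rules set questions 2 to 5 to missing, so the three work scores cannot be calculated. Question 6 is untouched, and activity impairment is 7/10 × 100 = 70%. Under the closing sentence of the section, the same answer is not relevant. Both cannot hold.

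**Step 3. Test each stated reason against activity impairment.**
- Relevance only to the employed: contradicted by Steps 1 and 2.
- Imputation is doubtful when employment is unknown: the formula uses only question 6, so not knowing question 1 creates no difficulty.

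Both reasons are sound for the three work scores. Neither reaches the fourth.

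**Step 4. What would otherwise apply?** Under Section 8.3.2, continuous other efficacy variables are imputed under the hypothetical estimand, and components of the primary endpoint by the reference-based method. The exceptions are WPAI-SHP, the two MRI scores and the EQ-5D-3L utility score.

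**Step 5. Who drops out under observed cases?** Section 4.2.1.10 excludes missing data and data collected after the treatment discontinuation date. Section 3.4 defines that date in the double-blind period as treatment end + 28 days + 3 days. Assume that treatment end is the last dose and that visits fall on their nominal days, counted from the first dose, with Week 16 at 16 × 7 = 112:
- Last dose at Week 12: 84 + 28 + 3 = 115. Since 112 is not after 115, the Week 16 value is kept.
- Last dose at Week 8: 56 + 28 + 3 = 87. Since 112 is after 87, the Week 16 value is dropped.

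The loss is therefore missed or unanswered Week 16 assessments plus values after the derived date. It does not extend to everyone who stopped treatment before Week 16.

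**The case against.** The strongest reply is that the disputed sentence explains a choice and is not a rule about who is scored. That is right. A reader might infer that non-workers are excluded from activity impairment, but the SAP nowhere instructs this. The operative rules derive the score from an answered question 6, and a non-worker's answer is an observed case. One could assume that 20% to 40% are not employed and compute a loss of 60 to 120 of 300 participants, with intervals wider by 1/√(1 − f), that is 1.12 to 1.29 times. Those shares are not in the documents, and the reading behind them is one the SAP does not direct, so the figures are no part of this point.

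A reader might also infer that every discontinuer is lost. The 28 + 3 day rule does not support that.

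It is fair to add that observed cases is applied consistently to WPAI in three places, and that the EQ-5D-3L utility score is also exempt from imputation although it has no employment condition. Imputation is thus the default but not universal, and one method for one questionnaire is defensible if the reason given fits. The hypothetical-estimand imputation also sets post-discontinuation values to missing, so it would recover no off-treatment outcomes. The documents do not show that the estimate would change materially.

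What remains is that the only reasons the SAP gives for exempting WPAI do not apply to one of its four scores.

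**Conclusion.** The contradiction is established from Section 8.3.1.10 alone. Its definite consequence is narrow: activity impairment is denied the SAP's default imputation on a ground that is false for it, and participants without a usable on-treatment Week 16 value leave that comparison. Restriction to the employed is a risk of misprogramming and not an instruction.

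The stakes are modest. WPAI is an exploratory variable outside the testing hierarchy, and Section 8.3.3 calls the p-values of these additional tests nominal. No primary or key secondary result is affected. The size of the loss cannot be stated, because the documents give neither the share not employed nor the share with missing Week 16 data. The point is still more than editorial, since correcting the premise removes the stated basis for the analysis method of a tested variable.

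**What to change.** 1. In Section 8.3.1.10, change the reference to questions 2 to 6 so that it reads questions 2 to 5, and state that percent activity impairment is derived for all participants whatever the answer to question 1.
2. Limit the imputation exclusion to the three work scores in Section 8.3.1.10, footnote d of Table 4-1 and Section 8.3.2.
3. Analyse activity impairment with the hypothetical-estimand multiple imputation of Section 4.2.1.7, with observed cases as supportive. Add its range to Table 4-2: question 6 runs from 0 to 10, so the score runs from 0 to 100.

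The cost is a few lines of SAP text and one more variable in imputation programs that other continuous endpoints already need. The small downside is that one questionnaire then uses two missing-data methods, which a table footnote can explain.
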